4.3.4.2 Discontinuation Criteria for Everolimus

As per the approved product label for everolimus, treatment should be continued as long as clinical benefit is observed or until unacceptable toxicity occurs.

For this protocol, subjects must permanently discontinue everolimus for:

- Any drug-related Grade 4 adverse event or laboratory abnormality, except for the following events which do not require discontinuation:
 - Grade 4 neutropenia \leq 7 days
 - Grade 4 lymphopenia or leukopenia
 - Isolated Grade 4 electrolyte imbalances/abnormalities that are not associated with clinical sequelae and are corrected with supplementation/appropriate management within 72 hours of their onset
- Any dosing interruption lasting $>$ 6 weeks with the following exceptions:
 - Dosing interruptions to allow for prolonged steroid tapers to manage drug-related adverse events are allowed. Prior to re-initiating treatment in a subject with a dosing interruption lasting $>$ 6 weeks, the BMS medical monitor or study director must be consulted. Tumor assessments should continue as per protocol even if dosing is interrupted.
 - Dosing interruptions $>$ 6 weeks that occur for non-drug-related reasons may be allowed if approved by the BMS medical monitor or study director. Prior to re-initiating treatment in a subject with a dosing interruption lasting $>$ 6 weeks, the BMS medical monitor or study director must be consulted. Tumor assessments should continue as per protocol even if dosing is interrupted.
- Any adverse event, laboratory abnormality, or intercurrent illness which, in the judgment of the Investigator, presents a substantial clinical risk to the subject with continued everolimus dosing.

4.3.5 Treatment of Nivolumab Related Infusion Reactions

Since nivolumab contains only human immunoglobulin protein sequences, it is unlikely to be immunogenic and induce infusion or hypersensitivity reactions. However, if such a reaction were to occur, it might manifest with fever, chills, rigors, headache, rash, pruritis, arthralgias, hypo- or hypertension, bronchospasm, or other symptoms. All Grade 3 or 4 infusion reactions should be reported within 24 hours to the BMS Medical Monitor or Study Director and reported as an SAE if criteria are met. Infusion reactions should be graded according to NCI CTCAE (version 4.0) guidelines.

Treatment recommendations are provided below and may be modified based on local treatment standards and guidelines, as appropriate:

For Grade 1 symptoms: (Mild reaction; infusion interruption not indicated; intervention not indicated)

Remain at bedside and monitor subject until recovery from symptoms. The following prophylactic premedications are recommended for future infusions: diphenhydramine 50 mg (or equivalent) and/or paracetamol 325 to 1000 mg (acetaminophen) at least 30 minutes before additional nivolumab administrations.

For Grade 2 symptoms: (Moderate reaction requires therapy or infusion interruption but responds promptly to symptomatic treatment [eg, antihistamines, non-steroidal anti-inflammatory drugs, narcotics, corticosteroids, bronchodilators, IV fluids]; prophylactic medications indicated for ≤ 24 hours)

Stop the nivolumab infusion, begin an IV infusion of normal saline, and treat the subject with diphenhydramine 50 mg IV (or equivalent) and/or paracetamol 325 to 1000 mg (acetaminophen); remain at bedside and monitor subject until resolution of symptoms. Corticosteroid or bronchodilator therapy may also be administered as appropriate. If the infusion is interrupted, then restart the infusion at 50% of the original infusion rate when symptoms resolve; if no further complications ensue after 30 minutes, the rate may be increased to 100% of the original infusion rate. Monitor subject closely. If symptoms recur then no further nivolumab will be administered at that visit. Administer diphenhydramine 50 mg IV, and remain at bedside and monitor the subject until resolution of symptoms. The amount of study drug infused must be recorded on the case report form (CRF). The following prophylactic premedications are recommended for future infusions: diphenhydramine 50 mg (or equivalent) and/or paracetamol 325 to 1000 mg (acetaminophen) should be administered at least 30 minutes before additional nivolumab administrations. If necessary, corticosteroids (recommended dose: up to 25 mg of IV hydrocortisone or equivalent) may be used.

For Grade 3 or Grade 4 symptoms: (Severe reaction, Grade 3: prolonged [ie, not rapidly responsive to symptomatic medication and/or brief interruption of infusion]; recurrence of symptoms following initial improvement; hospitalization indicated for other clinical sequelae [eg, renal impairment, pulmonary infiltrates], Grade 4: life-threatening; pressor or ventilatory support indicated)

Immediately discontinue infusion of nivolumab. Begin an IV infusion of normal saline, and treat the subject as follows: Recommend bronchodilators, epinephrine 0.2 to 1 mg of a 1:1,000 solution for subcutaneous administration or 0.1 to 0.25 mg of a 1:10,000 solution injected slowly for IV administration, and/or diphenhydramine 50 mg IV with methylprednisolone 100 mg IV (or equivalent), as needed. Subject should be monitored until the investigator is comfortable that the symptoms will not recur. nivolumab will be permanently discontinued. Investigators should follow their institutional guidelines for the treatment of anaphylaxis. Remain at bedside and monitor subject until recovery from symptoms. In the case of late-occurring hypersensitivity symptoms (eg, appearance of a localized or generalized pruritus within 1 week after treatment), symptomatic treatment may be given (eg, oral antihistamine or corticosteroids).

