4.3.4 Discontinuation Criteria

4.3.4.1 Discontinuation Criteria for Nivolumab

Nivolumab administration should be discontinued for the following:

- Any Grade ≥ 2 drug-related uveitis, eye pain, or blurred vision that does not respond to topical therapy and does not improve to Grade 1 severity within the re-treatment period OR requires systemic treatment
- Any Grade 3 non-skin, drug-related adverse event lasting > 7 days, with the following exceptions for laboratory abnormalities, drug-related bronchospasm, hypersensitivity reactions, and infusion reactions:
 - Grade 3 drug-related laboratory abnormalities do not require treatment discontinuation except:
 - ◆ Grade 3 drug-related thrombocytopenia > 7 days or associated with bleeding requires discontinuation
 - ◆ Any drug-related liver function test (LFT) abnormality that meets the following criteria require discontinuation:
 - AST or ALT > 5 - 10 x ULN for > 2 weeks
 - AST or ALT > 10 x ULN
 - Total bilirubin > 5 x ULN
 - Concurrent AST or ALT > 3 x ULN and total bilirubin > 2 x ULN
 - Grade 3 drug-related bronchospasm, hypersensitivity reaction, infusion reaction, uveitis or pneumonitis of any duration requires discontinuation
- Any Grade 4 drug-related adverse event or laboratory abnormality, except for the following events which do not require discontinuation:
 - Grade 4 neutropenia ≤ 7 days
 - Grade 4 lymphopenia or leukopenia
 - Isolated Grade 4 electrolyte imbalances/abnormalities that are not associated with clinical sequelae and are corrected with supplementation/appropriate management within 72 hours of their onset
- Any dosing interruption lasting > 6 weeks with the following exceptions:
 - Dosing interruptions to allow for prolonged steroid tapers to manage drug-related adverse events are allowed. Prior to re-initiating treatment in a subject with a dosing interruption lasting > 6 weeks, the BMS medical monitor or study director must be consulted. Tumor assessments should continue as per protocol even if dosing is interrupted.
 - Dosing interruptions > 6 weeks that occur for non-drug-related reasons may be allowed if approved by the BMS medical monitor or study director. Prior to re-initiating treatment in a subject with a dosing interruption lasting > 6 weeks, the BMS medical monitor or study director must be consulted. Tumor assessments should continue as per protocol even if dosing is interrupted.

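### Section 4.3.5: an infusion reaction that resolves, is restarted and recurs fits both the Grade 2 instruction and the Grade 3 definition, which point to different consequences for nivolumab

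*Protocol*

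**What the plan says.** Protocol Section 4.3.5 manages nivolumab infusion reactions by grade and says that grading follows NCI CTCAE version 4.0.

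- **Grade 2, definition:** "Moderate reaction requires therapy or infusion interruption but responds promptly to symptomatic treatment".
- **Grade 2, management:** stop the infusion and treat, then "restart the infusion at 50% of the original infusion rate when symptoms resolve". On recurrence: "If symptoms recur then no further nivolumab will be administered at that visit". After sentences on treating the recurrence and recording the amount infused, the paragraph continues: "The following prophylactic premedications are recommended for future infusions: diphenhydramine 50 mg (or equivalent) and/or paracetamol 325 to 1000 mg (acetaminophen) should be administered".
- **Grade 3, definition:** the criteria include "recurrence of symptoms following initial improvement".
- **Grade 3 or 4, management:** "nivolumab will be permanently discontinued". The opening of the section also asks for all Grade 3 or 4 reactions to be reported to the medical monitor or study director within 24 hours.

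Section 4.3.4.1 repeats the stop independently: "Grade 3 drug-related bronchospasm, hypersensitivity reaction, infusion reaction, uveitis or pneumonitis of any duration requires discontinuation". Section 3.5 makes it mandatory, because it lists the protocol-defined reasons in Section 4.3.4 among those for which subjects must come off investigational product.

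Section 4.3.5 also says that its treatment recommendations may be adapted to local standards. Sections 4.3.4.1 and 3.5 contain no such allowance.

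**The concern.** The Grade 2 paragraph provides for symptoms that return after a restart and limits the stop to the current visit. The next paragraph of the same section places a return of symptoms after improvement under Grade 3, where the stop is permanent. A site that stays within the Grade 2 paragraph may plan the next infusion with premedication. A site that reads on to the Grade 3 definition ends nivolumab.

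The first stake is subject safety and equal handling: on one path, a subject who meets a mandatory stopping rule is re-exposed. The second is the safety data. The path taken can affect whether the event is recorded as Grade 2 or Grade 3, whether the 24-hour report is made, and whether a discontinuation is recorded. These entries feed the worst-grade toxicity tables planned in Section 8.4.3.

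**Working it through.** No arithmetic applies, and the plan gives no figure to reproduce. The check is to follow one event through the text.

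**The event.** A Grade 2 reaction occurs. The infusion is stopped, symptoms resolve, the infusion restarts at half rate, and symptoms recur.

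| Step | Reading the Grade 2 paragraph (4.3.5) | Reading the Grade 3 definition (4.3.5) with 4.3.4.1 |
|---|---|---|
| Does the text cover the event? | Yes, it has its own sentence on recurrence after a restart | Yes, recurrence after improvement is a listed criterion |
| Rest of that visit | No more nivolumab | No more nivolumab |
| Later visits | Not ruled out; premedication for future infusions follows | Permanent discontinuation |
| 24-hour report | Not asked for at Grade 2 | Asked for |

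**Is recurrence a criterion in its own right?** The Grade 3 wording reads "recurrence of symptoms following initial improvement; hospitalization indicated for other clinical sequelae". Semicolons separate recurrence from the prolonged-reaction criterion before it and the hospitalization criterion after it. The natural reading is a list of alternatives, so recurrence alone is enough.

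**Does the event meet that criterion?** The restart is permitted only once symptoms resolve. Full resolution includes improvement, so a later return of symptoms is recurrence after improvement.

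**Does the Grade 2 text leave later dosing open?** The stop is expressly for that visit. The premedication sentence concerns Grade 2 reactions in general, including those that restart without trouble, but it does not exclude recurrent cases. Later dosing is therefore implied, though nowhere stated.

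**Does another passage decide?**
- The delay criteria (4.3.1.1) and the resumption criteria (4.3.3.1) do not address recurrence on restart.
- The local-standards clause covers the treatment recommendations in 4.3.5. It does not relax 4.3.4.1 or 3.5.
- The CTCAE instruction bears on the grade. It gives a site good reason to call the recurrent event Grade 3, but it leaves the recurrence sentence under the Grade 2 heading with its visit-only stop.

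The two texts agree for the visit itself and part company for every later visit.

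**The case against.** The strongest reply is that these are not two opposed commands. Stopping for that visit is a same-day instruction, and permanent discontinuation also satisfies it. No sentence says that a subject whose symptoms recurred may be dosed again. The section can be read in sequence: start under Grade 2, stop if symptoms return, and, if the event now meets the Grade 3 definition, apply the Grade 3 rule. Grading comes from one external scale, and the protocol lists recurrence only under Grade 3. On this view the defect is a missing cross-reference.

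Much of this stands. A reader might infer that the protocol orders continued dosing after a recurrence; it does not. A reader might also infer that nothing in the document bears on the grade; the CTCAE instruction does. But the sequential reading has to be supplied by the reader. If every recurrence is Grade 3, a recurrence instruction under Grade 2, limited to one visit and followed by advice for future infusions, is misplaced and invites the other reading. Nothing in 4.3.5 directs the site from that sentence to the Grade 3 definition.

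The reply is also right on scale. The affected subjects are those with a Grade 2 reaction, an interruption, a restart and a recurrence, far narrower than the nivolumab arm as a whole. Section 4.3.5 calls infusion reactions unlikely. The 296-subject Phase 1 summary in Section 1.4.5.1 names them neither among the most frequent drug-related events (at least 5%) nor among the most common Grade 3/4 ones (at least 1%), although the first list may not be exhaustive.

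**Conclusion.** The inconsistency is real but narrow. An infusion reaction that recurs after the restart fits both the Grade 2 recurrence sentence and the Grade 3 definition. The first implies that later dosing is possible; the second requires a permanent stop and a 24-hour report. For each subject concerned the difference is between continuing and ending nivolumab.

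This rests on two readings: that the Grade 3 criteria are alternatives, and that premedication for future infusions, given without exclusion, leaves later dosing open. The documents give no rate for recurrence after restart, so the number affected is unknown and is probably small.

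A reader might infer that the efficacy result is at risk. The documents do not support that. Overall survival runs from randomization to death (8.3.1) in all randomized subjects (8.2), so stopping nivolumab does not remove anyone from the primary analysis. Under Amendment 15 the interim results already stand as the final primary analysis. What remains is consistent handling and safety recording for Arm A subjects still on nivolumab and for former everolimus subjects entering the extension phase.

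**What to change.** Reconcile the recurrence sentence in the Grade 2 paragraph of 4.3.5 with the Grade 3 definition there and with the discontinuation rules in 4.3.5 and 4.3.4.1. The amended text should ensure that recurrence after a restart is graded once, under CTCAE version 4.0, and that the 24-hour report and the treatment consequence follow from that grade. The order matters: the grade should determine management, and a decision to continue or stop should not determine the recorded grade. How the passages are reconciled is for the sponsor's clinical team; this review takes no view on which clinical rule should apply.

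The cost is one or two sentences in the next amendment and a memo to sites, with no additional procedures or subjects.

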4.3.6 Continued Treatment Beyond Progression of Disease

As described in [Section 1.4.6.6](#), accumulating evidence indicates a minority of subjects treated with immunotherapy may derive clinical benefit from continued treatment despite initial evidence of progressive disease.⁴⁸ For this reason, subjects receiving nivolumab will be permitted to continue study therapy beyond initial investigator-assessed RECIST 1.1-defined progression as long as they meet the 2 criteria listed below. In addition, as the approved product label for everolimus allows for continued treatment as long as clinical benefit is observed or until unacceptable toxicity occurs, subjects on the everolimus arm will also be permitted to continue treatment beyond initial investigator-assessed RECIST 1.1-defined progression if they meet the same 2 criteria listed below.

Criteria for continuing treatment beyond initial investigator-assessed RECIST 1.1-defined progression:

- Investigator-assessed clinical benefit,
and
- Subject is tolerating study drug.

The assessment of clinical benefit should take into account whether the subject is clinically deteriorating and unlikely to receive further benefit from continued treatment.

All decisions to continue treatment beyond initial progression **must be discussed with the BMS Medical Monitor or Study Director and documented in the study records.**

Subjects will be re-consented with an ICF describing any reasonably foreseeable risks or discomforts.

Subjects should discontinue study therapy upon evidence of further progression, defined as an additional 10% or greater increase in tumor burden from time of initial progression (including all target lesions and new measurable lesions).

New lesions are considered measurable at the time of initial progression if the longest diameter is at least 10 mm (except for pathological lymph nodes, which must have a short axis of at least 15 mm). Any new lesion considered non-measurable at the time of initial progression may become measurable and therefore included in the tumor burden measurement if the longest diameter increases to at least 10 mm (except for pathological lymph nodes, which must have an increase in short axis to at least 15 mm).

For statistical analyses that include the investigator-assessed progression date, subjects who continue treatment beyond initial investigator-assessed, RECIST 1.1-defined progression will be considered to have investigator-assessed progressive disease at the time of the initial progression event.

Amendment 15 Update:

Subjects enrolled in the nivolumab extension phase will be permitted to continue study therapy beyond initial investigator-assessed RECIST 1.1-defined progression, as defined in this section.

4.4 Blinding/Unblinding

Not applicable.

4.5 Treatment Compliance

Treatment compliance will be monitored by drug accountability as well as the subject's medical record and eCRF.

4.6 Destruction and Return of Study Drug

4.6.1 Destruction of Study Drug

For this study, study drugs (those supplied by BMS or sourced by the investigator) such as partially used study drug containers, vials and syringes may be destroyed on site.

Any unused study drugs can only be destroyed after being inspected and reconciled by the responsible BMS Study Monitor unless study drug containers must be immediately destroyed as required for safety, or to meet local regulations (eg, cytotoxics or biologics).

On-site destruction is allowed provided the following minimal standards are met:

- On-site disposal practices must not expose humans to risks from the drug.
- On-site disposal practices and procedures are in agreement with applicable laws and regulations, including any special requirements for controlled or hazardous substances.
- Written procedures for on-site disposal are available and followed. The procedures must be filed with the site's SOPs and a copy provided to BMS upon request.
- Records are maintained that allow for traceability of each container, including the date disposed of, quantity disposed, and identification of the person disposing the containers. The method of disposal, ie, incinerator, licensed sanitary landfill, or licensed waste disposal vendor must be documented.
- Accountability and disposal records are complete, up-to-date, and available for the Monitor to review throughout the clinical trial period.

If conditions for destruction cannot be met the responsible BMS Study Monitor will make arrangements for return of study drug.

It is the investigator's responsibility to arrange for disposal of all empty containers, provided that procedures for proper disposal have been established according to applicable federal, state, local, and institutional guidelines and procedures, and provided that appropriate records of disposal are kept.

4.6.2 *Return of Study Drug*

If study drug will not be destroyed upon completion or termination of the study, all unused and/or partially used study drug that was supplied by BMS must be returned to BMS. The return of study drug will be arranged by the responsible BMS Study Monitor.

It is the investigator's responsibility to arrange for disposal of all empty containers, provided that procedures for proper disposal have been established according to applicable federal, state, local, and institutional guidelines and procedures, and provided that appropriate records of disposal are kept.

4.7 *Retained Samples for Bioavailability / Bioequivalence*

Not applicable

5 STUDY ASSESSMENTS AND PROCEDURES

5.1 Flow Chart/Time and Events Schedule

Table 5.1-1: Screening Procedural Outline (CA209025)			
Procedure	Screening^a	Day -3 to +1 (Post Randomization)	Notes
Eligibility Assessments			
Informed Consent	X		Obtain consent prior to performing any testing for eligibility.
Inclusion/Exclusion Criteria	X	X	All inclusion/exclusion criteria should be assessed prior to randomization
Medical History	X		Include assessment of Pulmonary Risk Factors
Tumor tissue samples	X		May be archival. 1 paraffin block or a minimum of 10 FFPE unstained slides received by Central Lab prior to subject randomization. (FNA and bone metastases samples not acceptable)
Tumor Assessments	X		CT or MRI within 30 days prior to first dose of study drug. Baseline imaging of chest, abdomen, pelvis, brain, and all known sites of disease is required.
Safety Assessments			
Physical Examination	X		Within 30 days of randomization
Vital Signs (including Performance status)	X	X	Screening visit should include weight, height and KPS. Complete vitals should be performed within 3 days prior to first dose of study drug to include: body weight, BP, HR, temperature, and oxygen saturation by pulse oximetry at rest and after exertion (Section 5.3)
Concomitant Medication Collection	X		Within 14 days prior to randomization
Assessment of Signs and Symptoms	X		Within 14 days prior to randomization
Urinalysis	X		Within 14 days prior to randomization to include: protein

Table 5.1-1: Screening Procedural Outline (CA209025)			
Procedure	Screening^a	Day -3 to +1 (Post Randomization)	Notes
Laboratory Tests	X		Local Labs: Within 14 days prior to randomization to include: CBC w/ differential, LFTs (AST, ALT, total bili, alk phosphatase), BUN or serum urea, creatinine, Ca, Mg, Na, K, Cl, albumin, endocrine panel (TSH, free T3, free T4), fasting serum lipids profile including total cholesterol, triglycerides, LDL, and HDL; fasting glucose and Hep B and C testing (HBV sAg, HCV Ab or HCV RNA).
Pregnancy Test	X	X	For WOCBP at screening and within 24 hours of the first dose of study drug (serum or urine) Local/site.
Exploratory Samples		X	Must be obtained prior to dosing. See Table 5.1-6
PGx sample (Optional)		X	Can be obtained at any time after PGx consent is signed
Clinical Drug Supplies			
Randomize		X	First dose of study medication must be administered within 3 working days of randomization.
Other			
Patient-Reported Outcome Measurements		X	After randomization and prior to first dose: FKSI-DRS and EQ-5D (Use Cycle 1 visit on ePRO tablet for this visit)

^a All testing listed to be performed within 30 days prior to randomization, unless otherwise specified
Note: Screening period is not limited to 30 days, provided testing is performed within time frames noted.

Table 5.1-2: On-Study Procedural Outline Arm A- Nivolumab (BMS-936558)				
Procedure	Each Cycle Day 1	2nd Dose of Cycle	Q 8 wks from Randomization	Notes
Safety Assessments				
Targeted assessments	X			Except Cycle 1. Assessments within 48 hrs of dosing to include: Targeted physical exam, performance status and weight. Oxygen saturation by pulse oximetry at rest and after exertion (Section 5.3).
Adverse Events Assessment	X	X		eSAEs should be approved in TAO by Investigator within 4 days from entry.
Concomitant Medications	X	X		Note: Immunosuppressive agents are recorded on a separate log page
Laboratory Tests	X			Cycle 2 and beyond: (within 72 hrs of dosing) CBC w/differential, LFTs, BUN or serum urea, creatinine. Even cycles only (within 72 hours of dosing): Fasting serum lipids profile (total cholesterol, triglycerides, LDL, and HDL), fasting glucose, and TSH (See Section 5.3).
		X		LFTS only (within 72 hours of dosing)
Pregnancy Test	X			For WOCBP Serum or urine (Note: perform q6 weeks if cycle start is delayed)
Study Samples				PK, Immunogenicity, soluble factors, miRNA, peripheral blood RNA and PBMC. See Table 5.1-5 and Table 5.1-6 for schedule of samples
Efficacy Assessments				
Tumor Assessments			X	By methods used at baseline. Tumor assessments at week 8, 16, 24, 32, 40, 48, and 56 (± 1 wk) from randomization, then every 12 wks (± 1 wk) until disease progression is documented or treatment is discontinued, whichever occurs later.

Table 5.1-2: On-Study Procedural Outline Arm A- Nivolumab (BMS-936558)				
Procedure	Each Cycle Day 1	2nd Dose of Cycle	Q 8 wks from Randomization	Notes
Clinical Drug				
Administer Study Treatment	X	X		Record study drug infusion start and stop times for nivolumab (Arm A). Doses of nivolumab should not be given less than 12 days from the previous dose. If the 2nd dose cannot be given within a 28 day window, it will be omitted and the next dose received will be Day 1 of the next cycle.
Other				
Patient-Reported Outcome Measurements	X			Prior to any study-related procedures: FKSI-DRS and EQ-5D
Health Resource Utilization	X			Except cycle 1. (Section 5.8.1)

Table 5.1-3: On-Study Procedural Outline Arm B- Everolimus			
Procedure	Each Cycle Q 4 Weeks Day 1	Q 8 wks from Randomization	Notes
Safety Assessments			
Targeted assessments	X		Except Cycle 1. Assessments within 48 hrs of dosing to include: Targeted physical exam, performance status and weight. Oxygen saturation by pulse oximetry at rest and after exertion (Section 5.3).
Adverse Events Assessment	X		eSAEs should be approved in TAO by Investigator within 4 days from entry.
Concomitant Medications	X		Note: Immunosuppressive agents are recorded on a separate log page
Laboratory Tests	X		Cycle 2 and beyond: (within 72 hrs prior to each new cycle) CBC w/differential, LFTs, BUN or serum urea, creatinine. Even cycles only (within 72 hours prior to each new cycle): Fasting serum lipids profile (total cholesterol, triglycerides, LDL, and HDL), fasting glucose, and TSH (See Section 5.3).
Pregnancy Test	X		For WOCBP Serum or urine (Note: perform q6 weeks if cycle start is delayed)
Efficacy Assessments			
Tumor Assessments		X	By methods used at baseline. Tumor assessments at week 8, 16, 24, 32, 40, 48, and 56 (± 1 wk) from randomization, then every 12 wks (± 1 wk) until disease progression is documented or treatment is discontinued, whichever occurs later.
Clinical Drug			
Administer Study Treatment	X		First dose of study medication must be administered within 3 working days of Randomization
Study Samples			Soluble factors, miRNA, peripheral blood RNA, PBMC See Table 5.1-5 and Table 5.1-6 for schedule of samples
Other			
Patient-Reported Outcome Measurements	X		Prior to any study-related procedures: FKSI-DRS and EQ-5D
Health Resource Utilization	X		Except cycle 1. (Section 5.8.1)

Table 5.1-4: Follow-Up Assessments (CA209025) - ALL Subjects			
Procedure	X or XX, Follow-Up Visit 1+ 2^a	Y or YY, Survival Follow-Up Visits^b	Notes
Safety Assessments			
Targeted Physical Examination	X		To assess for potential late emergent study drug related issues
Adverse Events Assessment	X		All new and continuing adverse events need to be documented and followed until 100 days after last dose (X02 or XX02 visit). If drug related events continue at second follow-up visit they need to be followed to resolution or until they are deemed irreversible by the investigator. eSAEs should be approved in TAO by Investigator within 4 days from entry.
Concomitant Medications	X		
Laboratory Tests	X		For X01 (and XX01) ONLY, repeat at X02 (and XX02) if study drug related toxicity persists. To include CBC w/ differential, LFTs, BUN, creatinine, fasting serum lipids profile (total cholesterol, triglycerides, LDL, and HDL), fasting glucose, and TSH
Pregnancy Test	X		Serum or urine
Survival Status			
Subject Status	X	X	Every 3 months (Y and YY Survival Follow-ups may be accomplished by visit or phone contact), to include subsequent anti-cancer therapy.
Efficacy Assessments			
Tumor Assessments	X	X	Only for subjects without progression on study therapy. Tumor assessments should be continued every 8 wks (\pm 1 wk) from randomization (or first dose of nivolumab for the nivolumab extension phase) for the first 12 months, then every 12 weeks (\pm 1 wk) until disease progression is documented
Study Samples Arm A Only			
PK Samples	X		See Table 5.1-5; Only for subjects ORIGINALLY randomized to Arm A, not required for nivolumab extension phase
Immunogenicity Blood Sample	X		See Table 5.1-5; Only for subjects ORIGINALLY randomized to Arm A, not required for nivolumab extension phase

Table 5.1-4: Follow-Up Assessments (CA209025) - ALL Subjects			
Other			
Patient-Reported Outcome Measurements	X	X	Collect FKSI-DRS and EQ-5D at both “X” and “XX” follow-up visits Collect EQ-5D information either in person or via telephone at “Y” and “YY” survival visits, q3 months for 1 year, then q6 months (sect. 5.3.1)
Health Resource Utilization	X		

^a X visits as follow, X1 = 30 days from last dose \pm 7 days, or may be on date of discontinuation \pm 7 days if the date of discontinuation is more than 37 days after last dose. X2 = 100-121 days from last dose (ie, 70-84 days from X1); XX01 and XX02 follow the same timeframe, but from last dose from the nivolumab extension phase

^b Y, Survival visits continue every 3 months after X visits; YY, Survival visits continue every 3 months after the XX visits (nivolumab extension phase).

Table 5.1-5: Pharmacokinetic and Immunogenicity Sampling Schedule for Subjects Originally Randomized to the Nivolumab Arm				
Study Day^a	Time (Relative to Dosing) Hour	Time (Relative to Dosing) Hour: Min	Pharmacokinetic Blood Sample Schedule	Immunogenicity Blood Sample Schedule
Day -3 to +1 (post randomization)	0 (Predose)	00:00		X
Cycle 1 Day 1	1.0 (EOI) ^b	01:00	X	
Cycle 1 Dose 2	0 (Predose)	00:00	X	X
Cycle 2 Day 1	0 (Predose)	00:00	X	
Cycle 3 Day 1	0 (Predose)	00:00		
Cycle 4 Day 1	0 (Predose)	00:00	X	X
Cycle 4 Day 1	1.0 (EOI) ^b	01:00	X	
Q 4th Cycle Day 1 ^c	0 (Predose)	00:00	X	X
Follow-up visit X 1 & 2			X	X

^a If a subject permanently discontinues study drug treatment during the sampling period, they will move to sampling at the follow up visits.

^b EOI: End of Infusion. This sample should be taken preferably within 2 minutes prior to the end of infusion. If the end of infusion is delayed to beyond the nominal infusion duration of 1 hour, the collection of this sample should also be delayed accordingly.

^c Every 4th cycle from cycle 4 until discontinuation of nivolumab. Predose ONLY. Example: cycle 8, 12, 16 etc.

Note: Predose samples can be obtained any time prior to starting administration on day of dosing for Cycle 1 Dose 2 and forward.

Table 5.1-6: Serum Sampling Schedule for All Subjects, Except in the Nivolumab Extension Phase						
Study Day	Time (Relative to Dosing) Hour	Time (Relative to Dosing) Hour: Min	Serum (for soluble factors and miRNA).	Peripheral Blood RNA	PBMC	Whole Blood (SNP)
Day -3 to +1 (post randomization; prior to dosing)	0 (Predose)	00.00	X	X	X	X
Cycle 2 Day 1	0 (Predose)	00.00	X	X	X	
Cycle 3 Day 1	0 (Predose)	00:00	X	X	X	

Note: Predose samples can be obtained any time prior to starting administration on day of dosing for Cycle 2 and Cycle 3 Day 1 samples

Table 5.1-7: Screening Procedural Outline (CA209025) For Subjects Previously Randomized to Everolimus Entering Nivolumab Extension Phase		
Procedure	Screening	Notes
Eligibility Assessments		
Informed Consent	X	
Inclusion/Exclusion Criteria	X	Assessed prior to calling IVRS and registering subject for extension phase
Medical History	X	
Safety Assessments		
Vital Signs and Oxygen Saturation	X	Temperature, BP, HR, RR, O ₂ saturation by pulse oximetry Obtain vital signs within 72 hours of first dose of nivolumab
Physical Examination (including Performance Status)	X	Includes Weight, and Karnofsky performance status Focused physical exam may be performed at screening, if clinically indicated
Laboratory Tests	X	Labs performed locally within 14 days prior to first dose of nivolumab (unless otherwise specified): CBC with differential, Serum chemistry (BUN or serum urea level, serum creatinine, sodium, potassium, calcium, magnesium, phosphate, chloride, and glucose), AST, ALT, total bilirubin, alkaline phosphatase, LDH, TSH, free T3, free T4
Pregnancy Test	X	Performed within 24 hours prior to first dose of nivolumab (serum or urine for WOCBP only)
Assessment of Signs and Symptoms	X	After obtaining Informed Consent, assess all signs and symptoms within 14 days prior to first dose of nivolumab
Concomitant Medication Collection	X	Within 14 days prior to first dose of nivolumab
Efficacy Assessments		
Radiographic Tumor Assessment (Chest, Abdomen, Pelvis)	X	Should be performed within 28 days prior to first dose of nivolumab. MRI of brain (with contrast, unless contraindicated) is required in subjects with a known history of brain metastases. Additional sites of known or suspected disease (including CNS) should be imaged prior to first dose of nivolumab.
Other		
Patient-Reported Outcome Measurements	X	Prior to first dose of nivolumab: FKSI-DRS and EQ-5D

Table 5.1-8: On-Study Procedural Outline (CA209025) For Subjects Previously Randomized to Everolimus Entering Nivolumab Extension Phase				
Procedure	Each Cycle Day 1	2nd Dose of Cycle	Q8 wks from First Dose of Nivolumab	Notes
Safety Assessments				
Targeted assessments	X			Except first cycle. Assessments within 48 hrs of dosing to include: targeted physical exam, performance status and weight. Oxygen saturation by pulse oximetry at rest and after exertion (Section 5.3).
Adverse Events Assessment	X	X		eSAEs should be approved in TAO by Investigator within 4 days from entry.
Concomitant Medications	X	X		Note: Immunosuppressive agents are recorded on a separate log page
Laboratory Tests	X			Cycle 2 and beyond: (within 72 hrs of dosing) CBC w/differential, LFTs, BUN or serum urea, creatinine. Even cycles only (within 72 hours of dosing): glucose, and TSH (with reflexive free T4/free T3). (See Section 5.3).
		X		LFTs only (within 72 hours of dosing)
Pregnancy Test	X			For WOCBP Serum or urine (Note: perform q6 weeks if cycle start is delayed)
Efficacy Assessments				
Tumor Assessments			X	By methods used at screening. Tumor assessments at Week 8, 16, 24, 32, 40, 48, and 56 (± 1 wk) from first dose of nivolumab, then every 12 wks (± 1 wk) until disease progression is documented or treatment is discontinued, whichever occurs later.

Table 5.1-8: On-Study Procedural Outline (CA209025) For Subjects Previously Randomized to Everolimus Entering Nivolumab Extension Phase				
Procedure	Each Cycle Day 1	2nd Dose of Cycle	Q8 wks from First Dose of Nivolumab	Notes
Clinical Drug				
Administer Study Treatment	X	X		Record study drug infusion start and stop times for nivolumab. Doses of nivolumab should not be given less than 12 days from the previous dose. If the 2nd dose cannot be given within a 28 day window, it will be omitted and the next dose received will be Day 1 of the next cycle.
Other				
Patient-Reported Outcome Measurements	X			Prior to any study-related procedures: FKSI-DRS and EQ-5D
Health Resource Utilization	X			Except cycle 1. (Section 5.8.1)

